### **7.2.8.2 Treatment Assignment**

Cohort assignment will be based presence of acquired resistance versus suboptimal benefit as defined under study entry/inclusion criteria.

### **7.2.8.3 Treatment Period**

Treatment period is 2 years or until progression.

### **7.2.8.4 Post-Treatment Visits**

#### **7.1.5.4.1 Safety Follow-Up Visit**

The mandatory Safety Follow-Up Visit should be conducted approximately 30 days after the last dose of trial treatment or before the initiation of a new anti-cancer treatment, whichever comes first. All AEs that occur prior to the Safety Follow-Up Visit should be recorded. Subjects with an AE of Grade > 1 will be followed until the resolution of the AE to Grade 0-1 or until the beginning of a new anti-neoplastic therapy, whichever occurs first. SAEs that occur within 90 days of the end of treatment or before initiation of a new anti-cancer treatment should also be followed and recorded. Subjects who are eligible for retreatment with pembrolizumab (as described in Section 7.1.5.5) may have up to two safety follow-up visits, one after the Treatment Period and one after the Second Course Phase.

### **7.2.8.5 Follow-up Visits**

Subjects who discontinue trial treatment for a reason other than disease progression will move into the Follow-Up Phase and should be assessed every 8-12 weeks ( $\pm$  7 days) by radiologic imaging to monitor disease status. After 1 year, the imaging time point will occur every 12-16 weeks ( $\pm$  7 days). Every effort should be made to collect information regarding disease status until the start of new anti-neoplastic therapy, disease progression, death, end of the study or if the subject begins retreatment with pembrolizumab as detailed in Section 7.1.5.5. Information regarding post-study anti-neoplastic treatment will be collected if new treatment is initiated.

Protocol #: UC IRB17-1539

Version Date: 1/23/2018

Subjects who are eligible to receive retreatment with pembrolizumab according to the criteria in Section 7.1.5.5 will move from the follow-up phase to the Second Course Phase when they experience disease progression.

#### **7.2.8.5.1 Survival Follow-up**

Once a subject experiences confirmed disease progression or starts a new anti-cancer therapy, the subject moves into the survival follow-up phase and should be contacted by telephone approximately every 12 to 16 weeks to assess for survival status until death, withdrawal of consent, or the end of the study, whichever occurs first OR at most 2 years out from the last patient receiving pembrolizumab.

#### **7.2.8.6 Second Course Phase (Retreatment Period)**

Subjects who stop pembrolizumab/epacadostat with SD or better may be eligible for up to one year of additional therapy with pembrolizumab + epacadostat if they progress after stopping study treatment. This retreatment is termed the Second Course Phase of this study and is only available if the study remains open and the subject meets the following conditions:

- **Either**

- Stopped initial treatment with pembrolizumab + epacadostat after attaining an investigator-determined confirmed CR according to RECIST 1.1, and
  - Were treated for at least 24 weeks with pembrolizumab + epacadostat before discontinuing therapy
  - Received at least two treatments with pembrolizumab and concurrent epacadostat (during that timeframe) beyond the date when the initial CR was declared

**OR**

- Had SD, PR or CR and stopped pembrolizumab/epacadostat treatment after 24 months of study therapy for reasons other than disease progression or intolerability

**AND**

- Experienced an investigator-determined confirmed radiographic disease progression after stopping their initial treatment with pembrolizumab/epacadostat
- Did not receive any anti-cancer treatment since the last dose of pembrolizumab/epacadostat

Protocol #: UC IRB17-1539

Version Date: 1/23/2018

- Has a performance status of 0 or 1 on the ECOG Performance Scale
- Demonstrates adequate organ function as detailed in Section 5.1.2
- Female subject of childbearing potential should have a negative serum or urine pregnancy test within 72 hours prior to receiving retreatment with study medication.
- Female subject of childbearing potential should be willing to use one of the following methods of contraception (*Intrauterine device (IUD)*, *Vasectomy of a female subject's male partner*, *Contraceptive rod implanted into the skin*), 2 other methods of birth control (as listed in below footnote) or be surgically sterile, or abstain from heterosexual activity for the course of the study through 120 days after the last dose of study medication (Reference Section 5.7.2). Subjects of child bearing potential are those who have not been surgically sterilized or have been free from menses for > 1 year.
- Male subject should agree to use an adequate method of contraception starting with the first dose of study therapy through 120 days after the last dose of study therapy.
- Does not have a history or current evidence of any condition, therapy, or laboratory abnormality that might interfere with the subject's participation for the full duration of the trial or is not in the best interest of the subject to participate, in the opinion of the treating investigator.

Subjects who restart treatment will be retreated at the same dose and dose interval as when they last received pembrolizumab. Treatment will be administered for up to one additional year.

Footnote: two of the following contraception methods are acceptable when used in combination:

The two birth control methods can be 2 barrier methods or 1 barrier method plus 1 hormonal method to prevent pregnancy. The following birth control methods are allowed during the study:

- Barrier methods:
  - Diaphragm with spermicide (cannot be used with cervical cap)
  - Cervical cap with spermicide (cannot be used with diaphragm)
  - Condom (male or female cannot be used together)
  - Copper intrauterine device (IUD)
  - Contraceptive sponge
- Hormonal methods:
  - Hormonal contraceptives (such as the birth control pill, skin patch, vaginal ring, or subcutaneous injection)

### 7.3 Assessing and Recording Adverse Events

An adverse event is defined as any untoward medical occurrence in a patient or clinical investigation subject administered a pharmaceutical product and which does not necessarily have to have a causal relationship with this treatment. An adverse event can therefore be any unfavorable and unintended sign (including an abnormal laboratory finding, for example),

Protocol #: UC IRB17-1539

Version Date: 1/23/2018

symptom, or disease temporally associated with the use of a medicinal product or protocol-specified procedure, whether or not considered related to the medicinal product or protocol-specified procedure. Any worsening (i.e., any clinically significant adverse change in frequency and/or intensity) of a preexisting condition that is temporally associated with the use of the Merck/Incyte products, is also an adverse event.

Changes resulting from normal growth and development that do not vary significantly in frequency or severity from expected levels are not to be considered adverse events. Examples of this may include, but are not limited to, teething, typical crying in infants and children and onset of menses or menopause occurring at a physiologically appropriate time.

Merck/Incyte product includes any pharmaceutical product, biological product, device, diagnostic agent or protocol-specified procedure, whether investigational (including placebo or active comparator medication) or marketed, manufactured by, licensed by, provided by or distributed by Merck/Incyte for human use.

Adverse events may occur during the course of treatment in clinical trials or within the follow-up period specified by the protocol, or prescribed in clinical practice, from overdose (whether accidental or intentional), from abuse and from withdrawal.

Progression of the cancer under study is not considered an adverse event unless it is considered to be drug related by the investigator.

All adverse events will be recorded from the time of first study drug administration through 90 days following cessation of treatment or if a subject initiates new anticancer therapy, whichever is earlier and at each examination on the Adverse Event case report forms/worksheets. The reporting timeframe for adverse events meeting any serious criteria is described in section 7.2.3.1.

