#### **4.2.3 Translational Rationale**

The micro-environmental changes responsible for resistance to PD-1/PD-L1 blockade are incompletely understood. We will evaluate baseline tissue (archival or freshly obtained) for evidence of factors that may correlate with acquired resistance/suboptimal benefit as related to the immune microenvironment/tumor inflammation/IDO.

HNSCC is a disease with oftentimes biopsy accessible tumors, and baseline biopsies are optional (if archival tissue is available) or mandatory if no archival tissue is available.

Core biopsies (3-5 cores) will be obtained at baseline as indicated (see above/eligibility). An on treatment biopsy at 2-4 weeks on treatment will considered / is optional and dependent on ability to safely biopsy the tumor. Also in patients who have benefit and subsequently progress (acquired resistance) a biopsy may be considered.

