### **7.3.3 Immediate Reporting of Adverse Events to Incyte and Merck**

#### **7.3.3.1 Serious Adverse Events**

A serious adverse event is any adverse event occurring at any dose or during any use of Merck/Incyte products that:

- Results in death;
- Is life threatening;
- Results in persistent or significant disability/incapacity;
- Results in or prolongs an existing inpatient hospitalization;
- Is a congenital anomaly/birth defect;
- Is a new cancer (that is not a condition of the study);

Protocol #: UC IRB17-1539

Version Date: 1/23/2018

- Is associated with an overdose;
- Is an other important medical event

Refer to Table 8 for additional details regarding each of the above criteria.

Any serious adverse event, or follow up to a serious adverse event, including death due to any cause other than progression of the cancer under study that occurs to any subject from the time of first dose of study drug through 90 days following cessation of treatment, or the initiation of new anti-cancer therapy, whichever is earlier, whether or not related to Merck/Incyte products, must be reported within 24 hours to the Sponsor and within 2 working days to Incyte/Merck Global Safety as described in section 10.7.

Non-serious Events of Clinical Interest will be forwarded to Incyte / Merck Global Safety and will be handled in the same manner as SAEs.

Additionally, any serious adverse event, considered by an investigator who is a qualified physician to be related to Merck/Incyte products that is brought to the attention of the investigator at any time outside of the time period specified in the previous paragraph also must be reported immediately to the Sponsor and to Merck /Incyte as described in section 10.7.

This study will be conducted under an IND held by [name] at the University of Chicago. Annual Progress Reports will be submitted as required by FDA. Additionally the IND holder will submit a copy of these reports to Incyte/Merck & Co., Inc. (Attn: Worldwide Product Safety; [contact]) at the time of submission to FDA.

All subjects with serious adverse events must be followed up for outcome.

The investigator must assess and record the relationship of each SAE to the specific study drug, and report this as described in section 10.7. The original copy of the SAE Report and the fax confirmation sheet must be kept at the study site.

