### **7.3.3.2 Events of Clinical Interest**

Selected non-serious and serious adverse events are also known as Events of Clinical Interest

(ECI) and must be reported within 24 hours to the PI as well as Incyte/Merck.

Protocol #: UC IRB17-1539

Version Date: 1/23/2018

For the time period beginning when the consent form is signed until treatment allocation/randomization, any ECI, or follow up to an ECI, that occurs to any subject must be reported within 24 hours if it causes the subject to be excluded from the trial, or is the result of a protocol-specified intervention, including but not limited to washout or discontinuation of usual therapy, diet, placebo treatment or a procedure.

For the time period beginning at treatment allocation through 30 days following cessation of treatment, any ECI, or follow up to an ECI, whether or not related to study products, must be reported within 24 hours.

Events of clinical interest for this trial include:

1. an overdose of one of the investigational products, as defined below under Definition of an Overdose for This Protocol and Reporting of Overdose, that is not associated with clinical symptoms or abnormal laboratory results.
2. an elevated AST or ALT lab value that is greater than or equal to 3X the upper limit of normal and an elevated total bilirubin lab value that is greater than or equal to 2X the upper limit of normal and, at the same time, an alkaline phosphatase lab value that is less than 2X the upper limit of normal, as determined by way of protocol-specified laboratory testing or unscheduled laboratory testing.\*

\*Note: These criteria are based upon available regulatory guidance documents. The purpose of the criteria is to specify a threshold of abnormal hepatic tests that may require an additional evaluation for an underlying etiology.

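### AE and SAE capture opens at the first dose, so a serious complication of a pre-dose study biopsy need not be recorded or reported

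*Combined protocol and SAP*

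**What the plan says.** Section 7.3 sets the AE window: "All adverse events will be recorded from the time of first study drug administration", running to 90 days after treatment stops, or until new anticancer therapy if that comes sooner. Section 7.3.3.1 sets the SAE window in the same way: "from the time of first dose of study drug through 90 days following cessation of treatment", with the same cut-off.

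The AE definition in 7.3 includes signs, symptoms or disease "temporally associated with the use of a medicinal product or protocol-specified procedure".

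On tissue, section 4.2.3 says that "baseline biopsies are optional (if archival tissue is available) or mandatory if no archival tissue is available", and adds: "Core biopsies (3-5 cores) will be obtained at baseline as indicated". Inclusion criterion 3 (5.1.2) accepts archival tissue or a new core biopsy at baseline. Footnote 1 of the flow chart (6.1) lets the PI waive the fresh sample in exceptional cases.

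Section 7.3.3.2 has a rule that starts at signed consent and runs to treatment allocation. It covers an ECI that leads to exclusion "or is the result of a protocol-specified intervention, including but not limited to washout or discontinuation of usual therapy".

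**The concern.** A tumor biopsy done because the protocol asks for it is a research risk to the patient. If it causes a serious bleed, an airway problem or an infection before Day 1, one would expect the trial's safety rules to require a record and a report. As written, both windows open only after the procedure is over. The same applies to harm from stopping a drug in order to enter: section 5.6.3 bars several medicines during screening as well as treatment, and 7.1.1.4.1 refers to protocol washouts.

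What is at stake is oversight of participant safety. The weekly review in 10.10 works from AE and SAE reporting, so harm that no rule requires to be reported may not reach it. The point concerns the start of the window only, not its end.

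**Working it through.** No formula applies. The check is whether any rule in the protocol would require a pre-dose biopsy complication to be recorded or reported.

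**Step 1: does the biopsy come before the first dose?** Yes. Tissue is an eligibility item (inclusion criterion 3), and section 10.6 requires pre-treatment evaluations to be complete before registration. Section 5.2 also has treatment start once PD-L1 status and cohort are known. Section 4.2.4.2 describes PD-L1 work as retrospective, so I do not rest the timing on the PD-L1 result; eligibility alone places the biopsy before dosing. The screening period is 28 days in 6.1 and 30 days in 7.2.8.1.

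**Step 2: take each rule in turn.**

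| Rule | When it opens | What it covers | Pre-dose biopsy bleed caught? |
|---|---|---|---|
| AE recording, 7.3 | First dose | All AEs | No |
| SAE reporting, 7.3.3.1 | First dose | All SAEs, related or not, except death from the study cancer | No |
| Early ECI rule, 7.3.3.2 | Consent to allocation | ECIs only | No: the two listed are overdose without symptoms and a combined transaminase and bilirubin rise |
| Later ECI rule, 7.3.3.2 | Allocation | ECIs only | No, same list |
| SAEs outside the window, 7.3.3.1 | Any time | SAEs judged related to Merck/Incyte products | Not plainly, see step 3 |
| Unexpected reactions, 10.7 | Not stated | Events with a causal link to the study agent | No |
| AE monitoring, 7.1.2.1, and expedited reporting, 10.7 | No start date | AEs through the study; SAEs on the study | Not stated |

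**Step 3: the product definition.** Section 7.3 defines a Merck/Incyte product broadly enough to name protocol-specified procedures. The sentence then restricts the list to items that the companies make, license, provide or distribute. A core biopsy performed by the site does not clearly meet that restriction, so the rule for SAEs at any time cannot be relied on to catch it.

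**Step 4: the flow chart.** As extracted, the adverse event row in 6.1 has no mark under screening and starts at Cycle 1. Section 5.3.6 places Day 1 treatment after that day's assessments, so a pre-dose review does exist. Nothing says that it looks back over screening, and an event found there would still predate the window in 7.3.

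No rule clearly requires the event to be recorded or reported. The optional biopsy at 2 to 4 weeks on treatment falls inside the window and is not affected.

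**The case against.** **The definitions may exclude undosed patients.** The AE definition opens by referring to a subject given a pharmaceutical product, and the SAE definition is tied to use of the companies' products. On that reading the window and the definition agree. This stands as far as it goes: a reader might infer that the protocol flatly contradicts itself, and the wording does not prove that. It does not close the gap, because procedure harm before dosing would then be left out by definition as well as by window.

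**General wording may be enough.** Sections 7.1.2.1 and 10.7 speak of recording through the study and of SAEs on the study. Neither gives a start date, and 10.7 refers back to SAEs as already defined. They do not displace the explicit start in 7.3 and 7.3.3.1.

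**Few patients may be biopsied.** This stands. Archival tissue is the first option in criterion 3; sections 7.1.2.6, 7.2 and 7.2.8.1 presuppose tissue stored from before curative treatment; and the PI can waive the fresh sample. A reader might want to put a number on those exposed out of the planned 30, but the documents give no proportion, and these sections point towards a low one.

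**The patient would not vanish.** A reader might infer that someone harmed at biopsy is swapped out as a zero-dose patient under 5.10 and disappears from the trial. The documents do not support that. Because 10.6 places registration after pre-treatment evaluations, such a patient would usually be a screen failure. Section 10.9 speaks of entering each consented patient in the database, and 5.10 keeps an intention-to-treat analysis as secondary. What is missing is a required AE or SAE record, not every trace of the patient.

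**Conclusion.** The point holds as a gap in the safety reporting rules. The stated start of both windows leaves a serious complication of a pre-dose study procedure without a clear duty to record or report it, and none of the other clauses reliably fills the gap. It is worth correcting because it concerns participant safety and the correction is cheap.

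Its size cannot be computed. It depends on how many patients lack archival tissue and are not granted a waiver, which the documents do not give and which may be small. The conclusion assumes that the explicit start dates govern over general wording, and that a site biopsy is not something the companies provide. The response-rate analysis and the two-stage rule in 8.1 are untouched, and the toxicity summary of dosed patients would not change.

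**What to change.** In 7.3 and 7.3.3.1, add that from signed consent to first dose any AE or SAE is recorded and reported on the same timelines if it results from a protocol-specified procedure or washout, or causes the patient to be excluded. This extends to AEs and SAEs the triggers that 7.3.3.2 already uses for ECIs, and carries them on from allocation to the first dose.

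State in 6.1 that the existing Cycle 1 pre-dose review covers the screening interval; no new visit or mark is needed. In 8.1, list these events separately from treatment-emergent toxicity. While editing 7.3, correct its pointer for the SAE timeframe: it cites 7.2.3.1, but the timeframe is in 7.3.3.1, and 7.2.3 describes the Nanostring work.

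The cost is a sentence in each of two sections, a flag on the case report form and a few extra pre-treatment entries. No dose, endpoint or sample size changes.

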### **7.3.1 Definition of an Overdose for This Protocol and Reporting**

For purposes of this trial, an overdose of pembrolizumab will be defined as any dose of 1,000 mg or greater ( $\geq 5$  times the indicated dose). No specific information is available on the treatment of overdose of pembrolizumab. Appropriate supportive treatment should be provided if clinically indicated. In the event of overdose, the subject should be observed closely for signs of toxicity. Appropriate supportive treatment should be provided if clinically indicated.

If an adverse event(s) is associated with (“results from”) the overdose of a Merck/Incyte product, the adverse event(s) is reported as a serious adverse event, even if no other seriousness criteria are met.

If a dose of Merck/Incyte products meeting the protocol definition of overdose is taken without any associated clinical symptoms or abnormal laboratory results, the overdose is reported as a non-serious Event of Clinical Interest (ECI), using the terminology “accidental or intentional overdose without adverse effect.”

Protocol #: UC IRB17-1539

Version Date: 1/23/2018

All reports of overdose with and without an adverse event must be reported within 24 hours to the Sponsor and within 2 working days hours to Incyte / Merck Global Safety as described below / in section 10.7.

### **7.3.2 Reporting of Pregnancy and Lactation**

Although pregnancy and lactation are not considered adverse events, it is the responsibility of investigators or their designees to report any pregnancy or lactation in a subject (spontaneously reported to them), including the pregnancy of a male subject's female partner that occurs during the trial or within 120 days of completing the trial completing the trial, or 30 days following cessation of treatment if the subject initiates new anticancer therapy, whichever is earlier. All subjects and female partners of male subjects who become pregnant must be followed to the completion/termination of the pregnancy. Pregnancy outcomes of spontaneous abortion, missed abortion, benign hydatidiform mole, blighted ovum, fetal death, intrauterine death, miscarriage and stillbirth must be reported as serious events (Important Medical Events). If the pregnancy continues to term, the outcome (health of infant) must also be reported.

All Serious Adverse Events (“SAE”), including pregnancy and lactation exposure, required to be reported pursuant to the Protocol shall be provided to Incyte and its representatives by Institution or Principal Investigator within twenty-four (24) hours of learning of the event as well as any additional reports agreed upon by Institution or Principal Investigator and Incyte. SAE Reports will be sent to [[contact]](mailto:[contact]). By sending to this e-mail address, the Incyte Pharmacovigilance group will receive copies of the reports. This process will be tested and established before the first patient is enrolled in the Study. Notwithstanding anything to the contrary herein, Institution will have the primary responsibility of reporting adverse events (“AE”) to regulatory authorities.”

Also see Section 10.7 for reporting to Merck Global Safety.

